An alternative strategy is to apply LTD-like stimulation to the medial prefrontal cortex (LTD-like mPFC rTMS (Strategy 2, Aim 2). This strategy is based on our understanding of functional neural architecture, wherein the SN is modulated by 2 other core networks: the executive control network (ECN) and the default mode network (DMN). As stated above, it is possible to attenuate activity in the SN through LTP-like TMS to the DLPFC, a node in the ECN. It is also possible to attenuate the SN through LTD-like TMS to the ventral medial prefrontal cortex (a node in the DMN). **The proposed study will be the first to employ a randomized, double-blind, sham-controlled design to parametrically evaluate the longitudinal effects of 16 days of rTMS to the DLPFC (Aim 1) or the MPFC (Aim 2) on self-reported pain and the brain's response to pain. This will be done in a cohort of patients recruited from the community as well as MUSC clinics with chronic lower back pain that have not been able to find adequate pain relief, whether or not they are using prescription opiates for 3 or more months.** Participants will be randomized to receive rTMS to the DLPFC (iTBS), MPFC (cTBS), or sham (50% at each site), using a Latin square randomization. Resting state connectivity will be collected 3 times: before the 1st day of TMS, after the 12th day of TMS, and before the 16th day of TMS (the last day administered).

Aim 1. Evaluate DLPFC rTMS as a tool to dampen pain and the engagement of the Pain Network. Hypothesis 1: DLPFC TMS will attenuate the baseline brain response to pain (Pain Network activity) and increase activity in the ECN when the patient is given instructions to ‘control’ the pain.

Aim 2. Evaluate MPFC rTMS as a tool to dampen pain and the engagement of the Pain Network. Hypothesis 1: MPFC TMS will also attenuate the baseline brain response to pain (Pain Network activity) but will not effect the ECN or SN when the patient is given instructions to ‘control’ the pain.

(Exploratory Aim): We will evaluate if there are rate-dependent effects between baseline SN connectivity with the ECN and DMN and the efficacy of each TMS strategy on subjective pain. Data will be analyzed by using multivariate pattern analysis (MVPA) (2014). While the primary outcomes will be MRI V1 vs V2, we will also examine the relative ‘durability’ of the effects on pain by comparing the MRI data at the end of all TMS visits between and within groups with factor analysis.

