4.0 Study Endpoints (if applicable)

Through this R21 mechanism we hope to be able to build upon the early success of this trial by including a rigorous, randomized, sham-controlled design which includes neuroimaging data necessary to understand mechanisms of action of these innovative new treatment approaches.

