10.0 Study Design / Methods

Multidisciplinary Team. We have assembled diverse talents to develop translational approaches to TMS treatment development for opiate dependence. Our team has extensive experience in: 1) TMS ([name]), 2) NIH trials in chronic lower back pain ([name], [name]), 3) pain management ([name]), 4) neuroimaging ([name]), and 5) statistical modeling ([name], [name]). In addition to providing critical effect size data for a planned R01, this grant will provide an opportunity for several MUSC trainees in the DART Resident research program ([name]), and a NIDA T32 ([name] [name]) to get hands-on training with neuroimaging, TMS, and opiate dependent individuals. [name] will serve as a scientific advisor and meet regularly with the team to provide insight on outcomes and patient recruitment.

Overview. The proposed study will be the first to employ a randomized, double-blind, sham-controlled design to parametrically evaluate the longitudinal effects of 16 days of rTMS to the DLPFC (Aim 1) or the MPFC (Aim 2) on self-reported pain and the brain's response to pain. This will be done in a cohort of patients recruited from MUSC clinics and the outer community with chronic lower back pain. Participants will be randomized to receive TMS to the DLPFC, MPFC, or sham (50% at each site), using a Latin square randomization. Resting state connectivity will be collected at each MRI scanning session.. Quantitative Pain Testing will be collected 12 times. MRI data will be collected 3 times: before the 1st visit of TMS, before the 12th visit of TMS, and before the 16th visit of TMS.

Table 1. Study Design. Aim 1&2 will be conducted in parallel.

^primary goal: evaluate 2 TMS strategies as tools to decrease acute pain and brain reactivity to pain.

^secondary goal: durability

Screening	Group Assignment	Induction Phase				Maintenance Phase				Follow Up Phase							
		Week 1	2	3	4	5	6	7	8	9	10	11	12	13	14	15	16
	TMS Sessions	XXX	XXX	XXX	XXX	X	X	X	X								
	Clinical Assessments	XXX	XXX	XXX	XXX	X	X	X	X	X	X	X	X	X	X	X	
	Quantitative Urinalysis	X	X	X	X	X	X	X	X	X	X	X	X	X	X	X	
	Quantitative Pain Testing	X	X	X	X	X	X	X	X	X	X	X	X	X	X	X	
	Neuroimaging				X				X								

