•**Assessments:** The primary dependent measures will be extracted from the Quantitative Sensory Testing for pain thresholds. Other assessments include: Brief Pain Inventory (BPI), the pain craving form, and subjective pain rating scales, delivered before and after TMS. Participants will also complete the Beck Depression Inventory (BDI-II), the Profile of Mood States (POMS), the Pittsburgh Sleep Quality Index (PSQI), the State-Trait Anxiety Inventory (STAI), and Barratt Impulsiveness Scale (BIS), which assesses anxiety and depression measures. Though these are not primary outcomes, the results will be used in post-hoc analyses of the data. All surveys will be filled out by the patient on tablet computers (Apple iPad/Microsoft Surface) and data entry will be done directly via Redcap Software. •**MRI scanning:** The MRI scanning session will last 30 minutes and will contain: 1) a high resolution anatomical image (T1-weighted MPRAGE (TR 1.9 sec, TE 2.26 ms, 2x GRAPPA, 1 mm isotropic)), 2) resting state functional connectivity (TA 7 minutes, voxel size: 2.5 x 2.5 x 2.5, TR = 2.6 s, TE = 25 ms, flip angle = 60°, FOV = 224 mm x 224 mm, matrix size = 64 x 64), **For each of the above strategies (Active rTMS or Active Sham) we will explore a**

series of SubAims designed to quantify the effects of rTMS on subjective pain, quantitative sensory testing, and brain reactivity to pain.

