SubAim 1: Evaluating Pain using Clinical Assessments Quantitative Sensory Testing (QST). Using the Medoc ATS thermal stimulator (Medoc Ltd Advanced Medical Systems, Ramat Yishai, Israel), 3 primary outputs will be compiled for each individual via the method of limits (54): sensory threshold, pain threshold, tolerance threshold. The thermode will be attached to the right forearm, and when the procedure begins it will begin heating from room temperature (32°C) at 0.2°C per second. Participants will indicate when they first detect the temperature change (sensory threshold), when it becomes painful (pain threshold), and when they can no longer tolerate the stimuli (tolerance threshold). When participants indicate tolerance, the operator will initiate rapid (>8°C per second) cooling. For safety, the thermode will be unable to exceed 51° and will initiate rapid cooling at that point. QST will be performed at two timepoints for each visit – prior to the initial MRI session and after the second MRI session. **Pain Questionnaire.** In order to evaluate current levels of pain, we will ask participants to rate their current level of pain and discomfort (scale, 0 through 10), each time the participant comes in (Table 1). On days where the individual receives rTMS, they will fill out this assessment before and after each session. **Pain and Craving Questionnaire:** In addition to the Pain Questionnaire above, participants will also rate their urge to use a pain reliever (Scale 0 – 10) and the amount they would be willing to pay for a pain reliever (In US Dollars). This questionnaire will be used at the same time during each intervention visit as the Pain Questionnaire (Table 2).

SubAim 2: Evaluating Pain using Neuroimaging Data At baseline we expect that people with chronic pain will have elevated activations in the Pain Network. This will be analyzed through the resting state connectivity network. Following sham stimulation, we do not anticipate a significant reduction of this response. Based on prior studies by our group in non-opiate dependent individuals, following LTP-like stimulation of the DLPFC, we expect a significant amplification of the DLPFC (% BOLD signal change), and a reduction of the Pain Network (dACC, anterior insula) reflecting the increased influence of executive processes. MPFC TMS however will likely not have as large of an effect on ECN engagement during the instruction to Control the pain.

Data Analysis Plan.

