A. Quantitative Pain Testing. Based on our pilot data, we expect an interaction between treatment (Real DLPFC or MPFC TMS vs. Sham) and time (Before vs. After rTMS) on the painfulness QST measure but no effect on sensory or tolerance levels. Alternative outcomes: It is possible that individuals will experience a small level of acute pain relief from their normal regimen of medication. We will be collecting information on opiate dose and timing at each visit to be used as potential covariates. Further, there is the possibility that pain tolerance will rise, possibly also reflecting improvements in executive function.

B. Qualitative Pain Assessment. We expect reductions in pain and discomfort when comparing active vs sham. However, based on prior data in opiate dependent individuals, we expect the effect size of DLPFC rTMS in to improve measures of Control but not measures of mood, whereas MPFC will have a larger effect on mood.

C. Neuroimaging. At baseline we expect that there will be elevated activations in the Pain Network in individuals with chronic pain. Following sham stimulation, we do not anticipate a significant reduction of this response. Based on prior studies by our group in non-opiate dependent individuals, following LTP-like stimulation of the DLPFC, we expect a significant amplification of the DLPFC (% BOLD signal change), and a reduction of the Pain Network (dACC, anterior insula) reflecting the increased influence of executive processes. MPFC TMS however will likely not have as large of an effect on ECN engagement during the instruction to Control the pain.

Alternative outcomes: Though pilot data suggest that a single treatment will acutely reduce self-reported pain, it is possible that the neural circuits in opiate dependent individuals do not have the same 'plasticity potential' as in controls. The results of the baseline cortical modulation assessment of pain (instruction to "control" the pain) will help resolve this alternative outcome. If we fail to replicate prior work showing DLPFC activation, this could reflect executive deficits (58), suggesting that the MPFC TMS will be more efficacious.

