Exploratory Analysis: We will evaluate if there are rate-dependent effects between baseline SN connectivity with the ECN and DMN and the efficacy of each TMS strategy on subjective pain. Data will be analyzed by using multivariate pattern analysis (MVPA) (2014). While the primary outcomes will be MRI V1 vs V2, we will also examine the relative ‘durability’ of the effects on pain by comparing the MRI data at the 1 month follow up between and within groups with factor analysis. **Integration of Brain based and Behavioral Based Outcomes with Gender and other Demographic Variables:** Finally, we will compare the relative efficacy of these two types of TMS using the behavioral and neuroimaging measures. Specifically, we will determine the effect sizes for DLPFC and MPFC (relative to sham) stimulation on reducing the 1) the neural and 2) behavioral responses to pain, as well as 3) changes in clinical assessment metrics (see Approach). We will investigate the role of baseline cortical responsiveness on the pain response, as well as how changes in that evoked response are related to changes in both pain and craving measures. This will be specifically addressed as a factor of gender as well, given that there are established differences in sensitivity to pain and prevalence of opiate dependence between men and women.

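### The plan gives conflicting statements of its primary outcome (QST in one place, MRI visit 1 versus visit 2 in two others), and nothing settles which one answers the Aims

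*Combined protocol and SAP*

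**What the plan says.** All references are to the combined protocol and SAP.

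- **Section 10.0, Assessments:** "The primary dependent measures will be extracted from the Quantitative Sensory Testing for pain thresholds". The same paragraph says that the mood, sleep and impulsiveness scales are not primary outcomes, so the word is being used to rank measures.
- **Section 10.0, Exploratory Analysis:** "While the primary outcomes will be MRI V1 vs V2". The Exploratory Aim in Section 1.0 has the same clause. In both places it is set against a later durability comparison.
- **Section 10.0, SubAim 1:** "3 primary outputs will be compiled for each individual via the method of limits (54): sensory threshold, pain threshold, tolerance threshold".
- **Section 10.0, Expected Outcomes A:** an interaction is expected "on the painfulness QST measure but no effect on sensory or tolerance levels". The same paragraph then allows that tolerance may rise and offers a favourable explanation for it.
- **Section 10.0, Table 1:** "primary goal: evaluate 2 TMS strategies as tools to decrease acute pain and brain reactivity to pain", which covers both domains.
- **Section 4.0, Study Endpoints:** one sentence, beginning "Through this R21 mechanism we hope to be able to build upon the early success of this trial". It names no endpoint.
- **Section 10.0, Data Analysis Plan A and B:** time-by-treatment repeated-measures tests in which the grouping factor is real or sham stimulation. Both paragraphs say that a hypothesis is to be tested, and both give the purpose of the pilot as developing effect sizes for a later grant.
- **Section 10.0, Exploratory Analysis:** effect sizes relative to sham are promised for each stimulation site.

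**The concern.** The two statements of what is primary do not agree, and the section that should decide between them is silent. Three things are left open: which measure is primary, which time points define the effect, and whether the two active arms are pooled or each compared with sham. No testing order or adjustment appears in the documents.

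Two things are at stake. First, a report could lead with whichever candidate came out best and truthfully call it primary. Second, the trial exists to supply an effect size for the next one. An effect size picked as the best of several candidates is biased upward, and the next trial would then be too small.

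**Working it through.** **1. The plan's own figure.** Section 10.0 (Sample size estimate) gives effect sizes from 0.70 (thalamus) to 1.08 (insula) and says n=15 yields 80% power at two-sided p<0.05. For a two-sample t-test with n per group, df = 2n − 2 and the noncentrality is d·√(n/2).

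- d = 1.08, n = 15: noncentrality 1.08 × √7.5 = 2.96, power 81.5%. Fifteen per group is the smallest size that reaches 80%.
- d = 0.70, n = 15: power 45.7%; 80% needs 34 per group.
- A paired test with n = 15 gives 71.3% at d = 0.70 and reaches 80% at about d = 0.78.

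So, as a between-arm figure, n=15 reproduces only at the top of the stated range. The estimate rests on heat-pain task fMRI in regions of interest. It is neither a QST threshold nor resting-state connectivity, so it does not reveal which outcome was meant as primary.

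**2. Candidate families.** The documents allow at least three readings:

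- pain threshold plus one MRI measure;
- the three QST thresholds;
- the three thresholds plus one MRI measure.

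One MRI measure is a minimum, because Data Analysis Plan C names three networks. Each family is shown with the active arms tested separately against sham and with them pooled.

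**3. Chance of at least one false positive.** Inputs: 16 per arm (Sample size estimate) and a shared sham arm. Assumptions: every test at two-sided 5%, a level that appears only in the sample-size text; a common correlation r between measures, which the documents do not give; normal data with no true effect. For k independent tests the chance is 1 − 0.95^k. The other columns come from simulation (200,000 runs per cell).

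| Family | Tests, separate / pooled | Independent tests | Separate, r = 0.7 / 0.5 / 0.3 | Pooled, r = 0.7 / 0.5 / 0.3 |
|---|---|---|---|---|
| One measure | 2 / 1 | 9.75% / 5% | 9.0% at any r | 5.0% at any r |
| Pain threshold + one MRI | 4 / 2 | 18.5% / 9.75% | 15.1 / 16.3 / 16.8% | 8.4 / 9.2 / 9.4% |
| Three thresholds | 6 / 3 | 26.5% / 14.3% | 19.4 / 22.0 / 23.7% | 11.0 / 12.6 / 13.7% |
| Three thresholds + one MRI | 8 / 4 | 33.7% / 18.5% | 23.0 / 27.1 / 29.9% | 13.3 / 15.8 / 17.3% |

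**4. Cost of control.** With one primary measure and two active-versus-sham tests, Holm compares the smaller p-value with 0.025 and, if that succeeds, the larger with 0.05. The family-wise error is then at most 5%. Two-sample power with 16 per arm:

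- at alpha 0.05: 84.0% for d = 1.08 and 48.3% for d = 0.70;
- at alpha 0.025: 75.3% and 36.5%. Reaching 80% would need 18 and 41 per arm.

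**The case against.** The best defence is that this is a pilot. The Data Analysis Plan says twice that its purpose is to develop effect sizes, and it sets neither an alpha level nor a success criterion for any outcome. If nothing is declared a success, an inflated error rate has little to act on. This stands in part: it reduces the multiplicity concern. It does not remove it, because the same paragraphs say that hypotheses are to be tested, and it does not touch the selection of an effect size.

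The wording can also be read more kindly. SubAim 1 may mean only that the device yields three outputs; Data Analysis Plan A calls the same three simply output variables, and Expected Outcomes A predicts an effect on painfulness alone. The MRI clause sits in exploratory text and may mean the main MRI time contrast as opposed to durability. The real-or-sham grouping factor may mean that the active arms are pooled. Each reading is plausible and none is stated.

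A reader might infer that the plan sets up four co-primary measures, each tested at 5% in two contrasts, with success open on any of them. The documents do not support that. The 5% level appears only in the sample-size text, no success rule exists, the count of four takes the least favourable reading of the three outputs, and two contrasts per measure is one of two readings of the grouping factor.

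**Conclusion.** The conflict is real and stands in current text: QST is primary in Assessments, MRI visit 1 versus visit 2 is primary in the Exploratory Aim and Exploratory Analysis, and nothing reconciles them. It remains even if the three QST outputs are read as mere device outputs.

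Its size depends on the reading. Taking only pain threshold and one MRI measure, the chance of a false positive is about 15–17% with the arms separate and 8–9% with them pooled. The widest family considered gives 23–30% and 13–17%. All of this assumes testing at two-sided 5% and correlations of 0.7 to 0.3. The figures show what an unrestricted choice could cost; they are not the error rate of a stated rule.

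Because the trial is a pilot with no declared success criterion, this should be corrected before data are examined, but it does not invalidate the design.

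**What to change.** In Section 4.0, name one primary measure, one time contrast (baseline to end of induction) and one arm comparison. Bring the Exploratory Aim in Section 1.0 and the Assessments, SubAim 1, Data Analysis Plan and Exploratory Analysis text in Section 10.0 into line. The second scan needs a single definition: Section 1.0 places it after the 12th TMS day, and the Section 10.0 Overview before the 12th visit. Label every other measure secondary or exploratory and report it with a 95% confidence interval.

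The choice of measure is the sponsor's:

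- **QST heat pain threshold** fits Assessments and Expected Outcomes A. The documents give no QST effect size, so the existing power estimate would not apply to it.
- **One named MRI measure** is closer to Hypothesis 1 under both Aims. The existing estimate is for task fMRI, so its relevance to a resting-state measure would have to be argued.

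If each active arm is tested against sham, apply Holm across the two tests. Alternatively, state that the trial is estimation-only, with intervals and no success claim; this fits the stated pilot purpose and needs no adjustment, but the effect size to be carried forward must still be named in advance.

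The change is to wording only; no visit or procedure is affected. The cost to disclose is power: at alpha 0.025 with 16 per arm, about 75% at d = 1.08 and 37% at d = 0.70, against 84% and 48% at alpha 0.05. The other measures also lose any claim to be primary.

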performed using Statistical Parametric Mapping 12 (SPM12) in Matlab 2013 (Mathworks). Functional data will be corrected for magnetic field inhomogeneity and realigned (rigid-body, minimizing least squares differences) to the first image in the time series (Realign: Estimate and Unwarp). Non-linear deformations required for standard space normalization will be derived from each participant's anatomical image via a unified segmentation approach (Segment). After the mean realigned and unwarped functional image is coregistered to the skull stripped anatomical image (Coreg: Estimate) forward deformations (subject space to MNI standard space) will be applied (Normalise: Write). Finally, the data will be smoothed by an 8 mm full width half maximum Gaussian smoothing kernel (Smooth). Within-subject and between-group modeling. Data will be analyzed at the subject level using multivariate pattern analysis (Wager et al 2013 "An fMRI-Based Neurologic Signature of Physical Pain" new England Journal of Medicine). The six motion parameters (translations and rotations) will be included in the design matrices as covariates to account for non-task signal. The hot and warm blocks of thermal stimulus, as well as rating events, will be separately modeled in a boxcar fashion. Resting State Connectivity will be measured to compare MRI scan 1 to scan 2 – immediately after the treatment. MRI scan 3 will also be compared to these scans to see if there is a sustainable reduction in pain activity between these networks. Additionally factor analysis will be used to investigate the durability of the effects of each strategy on functional connectivity in each of the 3 Core networks (SN, ECN, DMN) using factor analysis longitudinally. **Covariates:** As an exploratory analysis we will also quantify the impact of several covariates which have previously been documented to affect the brain response to pain and pain thresholds (sex, Becks Depression Inventory score, length of time using chronic opiates). Although all participants will have taken their daily dose of opiates, which has a stable pharmacokinetic profile, we will also consider time since last dose.

Expected (and alternative) Outcomes:

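### The listed MRI session has no pain task, yet the imaging model, parts of Hypothesis 1 and the only power statement need one; the text does not settle whether a task is run

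*Combined protocol and SAP*

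**What the plan says.** **What is acquired.** In section 10.0 (General Methods, MRI scanning) the protocol states: "The MRI scanning session will last 30 minutes and will contain: 1) a high resolution anatomical image". The second and last item is a 7-minute resting-state run, after which the list stops on a comma. Section 1.0 says "Resting state connectivity will be collected 3 times", and the Overview in section 10.0 says "Resting state connectivity will be collected at each MRI scanning session". SubAim 2, on elevated Pain Network activation, adds: "This will be analyzed through the resting state connectivity network".

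**What the analysis and hypotheses use.**
- Data Analysis Plan, part C: "The hot and warm blocks of thermal stimulus, as well as rating events, will be separately modeled in a boxcar fashion".
- Section 1.0, Aim 1: DLPFC stimulation will "increase activity in the ECN when the patient is given instructions to" control the pain.
- Section 1.0, Aim 2: MPFC stimulation "will not effect the ECN or SN when the patient is given instructions to" control the pain. SubAim 2 and the Expected Outcomes return to this instruction. The Expected Outcomes also use a baseline assessment made under it to help interpret a failure of the circuits to respond.
- SubAim 2, repeated in the Expected Outcomes: "we expect a significant amplification of the DLPFC (% BOLD signal change").
- Sample size estimate (section 10.0, Participants): effect sizes of 0.70 (thalamus) to 1.08 (insula) come from a heat-pain-versus-rest contrast in 18 healthy controls. They are said to have done the same fMRI pain paradigm as this study. The plan concludes that n=15 gives 80% power at two-sided 0.05.

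**The concern.** A resting-state run has no stimulus blocks, no ratings and no instruction to control pain. If the session is only what is listed, the first-level model in part C has no events to model and the pain-control clause in each aim has no data source. The expected percent signal change in the DLPFC would also have no source, because a connectivity measure does not yield one. The only power figure would describe a measurement the trial does not make.

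If a task is run, the protocol omits its stimulus levels, block timing, ratings, instruction and acquisition settings. Part C could then not be carried out from the document.

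Either way, leaving the choice until the images are in hand would let the imaging outcome be picked after seeing the data.

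**Working it through.** **1. Sections side by side (all in 10.0 unless stated).**

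| Element of the plan | Needs | Supplied by the listed session? |
|---|---|---|
| Resting-state scan 1 v scan 2 (Data Analysis Plan C) | Resting-state run | Yes |
| Pain Network part of Hypothesis 1 (1.0), read through SubAim 2 | Resting-state run | Yes, on that reading |
| Hot blocks, warm blocks, rating events (Data Analysis Plan C) | Heat task with ratings | No |
| Pain-control clauses (1.0, SubAim 2, Expected Outcomes) | Task with that instruction | No |
| DLPFC percent BOLD change (SubAim 2, Expected Outcomes) | Evoked signal | No |
| Power basis (Sample size estimate) | Heat-pain-versus-rest contrast | No |

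The only heat procedure described is QST under SubAim 1. It is a forearm ramp that the participant ends at tolerance, not a block design. Its timing sentence places it before and after MRI sessions. That sentence is hard to square with a plan of three MRI visits, so I put no weight on it.

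**2. Reproducing the plan's power figure.** Inputs: d = 0.70 to 1.08, n = 15, two-sided alpha 0.05. The plan names neither the test nor the effect size used. I used the noncentral t distribution without multiplicity adjustment.

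- Two-sample, n per group: noncentrality = d × √(n/2), df = 2n − 2.
  - d = 1.08: 1.08 × √7.5 = 2.96, power 81%. Solving for 80% gives n = 14.48, so 15 per group. This matches the plan.
  - d = 0.70: 0.70 × √7.5 = 1.92, power 46%.
- Paired, n in one group: noncentrality = d × √n, df = n − 1.
  - d = 1.08: 1.08 × √15 = 4.18, power 97%.
  - d = 0.70: 0.70 × √15 = 2.71, power 71%.
- With n = 15, exactly 80% power needs d = 1.06 (two-sample) or 0.78 (paired).

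The figure therefore holds as a two-sample calculation at the top of the range and falls short at the bottom under either test. In every case d belongs to a heat-evoked contrast.

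**3. What can be said for resting-state data.** The documents give no effect size or SD for a connectivity measure, so its power cannot be computed. Precision can be given in SD units. For change in one real arm versus sham with the planned 16 per arm, the 95% CI half-width is t(0.975, 30) × √(2/16) = 2.042 × 0.354 = 0.72 SD of change. This is a generic result for 16 versus 16. It illustrates a replacement statement and does not measure the defect.

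**The case against.** The strongest reply is that a task is run and one list item was lost. The sample size paragraph speaks of the present study's own pain paradigm, part C names its regressors, and Table 1 gives brain reactivity to pain as part of the primary goal. The session lasts 30 minutes, of which the resting run takes 7, and the list breaks off on a comma; an item may even have been lost when the text was read from PDF. The Overview's sentence on resting-state data does not say that nothing else is collected. All of this stands, so a reader who infers that no task exists, and that the imaging hypotheses are untestable, goes further than the documents allow. What it does not remove is SubAim 2, which routes Pain Network activation through resting-state connectivity, or the absence of any description of the task elsewhere.

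A second reply is that this is a pilot for effect sizes and that the Assessments paragraph takes its primary measures from QST, which needs no scanner. That limits the damage. But section 1.0 and the Exploratory Analysis call the first-to-second MRI comparison primary, so imaging cannot be set aside as secondary, and a pilot still has to define the effect it estimates.

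A reader might also infer that the trial is underpowered. That is not supported: the plan's figure reproduces at its upper effect size, and for resting-state change there is nothing in the documents to compute power from.

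**Conclusion.** The concern holds as an internal contradiction that must be resolved before imaging data are analysed. As written, the block model cannot be fitted to the listed scan, and the only power statement concerns a contrast which that scan does not produce.

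Its reach is limited to the task-based imaging claims and the sample-size basis. QST, the questionnaires and the resting-state comparison of scan 1 with scan 2 can proceed, so the trial as a whole is not undermined. How much weight the imaging carries also depends on the unresolved disagreement over whether QST or MRI is primary.

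In size, n=15 gives 81% power for a two-sample effect of 1.08, but 46% (two-sample) or 71% (paired) at 0.70. These figures assume the noncentral t, equal groups in the two-sample case, and no multiplicity adjustment. Whether a task is run is left open because the text does not decide it.

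**What to change.** Check the scanner protocol for a task run. Then bring section 1.0 and, within section 10.0, the sample size estimate, MRI scanning list, SubAim 2, Data Analysis Plan C and Expected Outcomes into line in one direction before imaging data are analysed.

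- **If no task is run:** remove the block model, the pain-control clauses and the expected percent signal change. Restate the imaging hypotheses as a scan 1 to scan 2 change in a prespecified resting-state connectivity measure, each real arm versus sham. A measure among the three networks already named (SN, ECN, DMN) is one reasonable choice. State that the 0.70 to 1.08 effect sizes and n=15 for 80% power do not apply to it. Give precision instead, for example a half-width of 0.72 SD of change with 16 per arm, which suits the stated purpose of developing effect sizes.
- **If a task is run:** add it to the scan list with its stimulus, timing, ratings and control instruction. Keep the block model, and say which test and which effect size n=15 refers to.

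The cost is one amendment. Section 13.0 requires NIDA approval for protocol changes and refers to IRB amendments. No visits are added. If no task is run, the sponsor gives up the task-based claims and the present imaging power basis; if one is run, the change is added description and a clarified power statement.
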